Objective 1: To evaluate the comparative effectiveness of patient-centered messages to enhance clinical trial participation, through a culturally tailored website, accessed using iPads, versus NYU's standard clinical trial participation website.

Hypothesis 1: Participants exposed to tailored messages about clinical trial literacy will exhibit greater likelihood in participating in clinical trials than those exposed to NYU's standard website.

Objective 2: To determine whether psychosocial factors (awareness of clinical trial, intrinsic motivation, health literacy, and self-efficacy) and medical factors (risk behavior, history of preventive behavior, and clinical diagnoses) mediate greater likelihood of participating in clinical trials among individuals exposed to the intervention.

[figure not shown]
Hypothesis 2: Greater likelihood of participating in clinical trials will be mediated by greater health literacy and self-efficacy independent of other individual-level factors (medical, knowledge, attitude/beliefs, and intrinsic motivation) and contextual-level factors (social support and socio-economic position).

Study Design

Objective 1: To evaluate the comparative effectiveness of a culturally and linguistically tailored clinical trial literacy website in increasing likelihood of participating in clinical trials. To achieve this objective, we will use a randomized group design, assessing the following patient-centered outcomes: willingness to enroll in clinical trials and behavioral intent as well as likelihood of referring others to enroll in such trials) before and after exposure to a culturally-tailored clinical trial literacy website. Health literacy will be measured both before and post exposure to tailored messages.

Participants will be randomized into two groups. The intervention group (n=50) will have access to culturally tailored website. Participants in the control group (n=50) will have access to NYU 's standard trial participation website.

Study Flowchart

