Participants randomized to the control condition will have free access to the NYU standard clinical trials website. Currently, there is no specific comparative effectiveness data evidencing superiority of any website or other format for increasing clinical trials literacy. Furthermore, there has been previous research to suggest the overall difficulty that patients have in using generic, versus tailored clinical trial materials. This, our study will ascertain effectiveness of a tailored website compared to the standard website. Participants in the control condition will have access to the tailored website at the date of study completion (no later than 6 months' post-date of enrollment).

2. Process of Consent

We will explain to participants that the purpose of the study is to understand barriers pertaining to why blacks do not participate in clinical trials, assess their willingness to enroll in clinical trials, and ascertain whether or not they will refer others to participate in such trials. We will obtain participants consent to audio-record the debriefing session. The screening team will comprise ethnically concordant investigator: [name]. All participants will be reminded that their responses are confidential and that they may refuse to participate in the project or withdraw at any time without explanation, and further, that such action will in no way affect their future interactions with their health care provider, or with New York University Medical Center. To ensure confidentiality, data will be associated with an individual participant only by an assigned identification number, the code for which will be kept in a locked drawer that only the study investigators will have access to.

3. Number of subjects.

The proposed study expects to recruit a total of 100 participants from all recruitment strategies over a period of 9 months.

4. Gender of Subjects.

The study will include black men and women

5. Age of Subjects.

The sample frame will include black men and women 18 years old and older.

6. Racial and Ethnic Origin.

Our emphasis on blacks is justified by the low participation in clinical trials in this group.

7. Inclusion Criteria.

Self-reported race/ethnicity as African American, African, Caribbean American or black men and women; ages ≥ 18 years; accessible by telephone; no plans to move away from the region within the year following enrollment; consent to participate.

8. Exclusion Criteria.

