Medical Outcomes Study Short Form 36	X		
Internet Self-efficacy Scale	X	X	X
Clinical Trials Literacy	X	X	X

Message Effectiveness Scale		X	X
Clinical Vignette			X

IV. DATA ANALYSIS AND DATA MONITORING

Throughout the study, [name] will oversee data entry and verification, ensure adherence to coding, clean and edit protocols. Data will be maintained on a password-protected PC with backup copies kept on external disks in a secured location.

Participant-identifying information will be kept in a locked file cabinet with only numerical identifiers in computer files.

Hypothesis 1: Participants exposed to tailored messages about clinical trial literacy will exhibit greater likelihood in participating in clinical trials than those exposed to NYU's standard website. Secondly, we expect them to show greater likelihood to refer others to clinical trials as well.

Analysis: While the primary goal of the study is to develop and test effectiveness of tailored messages to overcome identified barriers to participating in clinical trials, the secondary goal is to examine factors likely to facilitate adoption of such messages. All participants in the intervention arm will have been exposed to all tailored web-based messages. To compare participants who exhibited improvement in health literacy and those who did not 2-months post-enrollment, t-tests and chi-squared tests will be used. Baseline subjective factors will be entered in a logistic regression model in order to determine which factors are associated with higher likelihood of (a) registering to participate in clinical trials, contrasting individuals in the two study arms and (b) referring others to participate as well. Multivariate analysis of covariance will be used to assess effects of messages on the secondary outcome: health literacy scores; effects of sociodemographic confounders will be adjusted.

Hypothesis 2: Greater likelihood of participating in clinical trials will be mediated by greater health literacy and/or self-efficacy independent of other individual-level factors (medical, knowledge, attitude/beliefs, and intrinsic motivation) and contextual-level factors (social support and socio-economic position).

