Analysis: We will examine the path toward greater participation in clinical trials using Structural Equation Modeling (SEM). SEM will determine influences of mediating/moderating factors on the role of tailored messages in improving participation rates in existing clinical trials. Specifically, we will use moderated path analysis from Baron and Kenny's model. We chose these factors based on research showing acceptable effect size in predicting likelihood of increased participation. Alternatively, we will employ probabilistic modeling methods (e.g., Bayesian Belief Network) to investigate interactions (omni-directionality) among predictors and different pathways to the desired study outcomes, determining which factors best differentiate cases and controls. Thus, we will ascertain patient characteristics most likely to show improvement in rates of participation.

V. STATISTICAL PLAN

Power Calculations: Primary Objective: Assuming a medium effect size ($d = 0.32$), as derived from Cohen, and a sample size of 100, the study will be adequately powered (> 80%) to detect significant differences between participants likely to show improvement in health literacy scores and those who are not using Fisher's Exact tests (critical $X^2 = 6.58$). This will also permit detection of a significant increase in the number of participants in the intervention arm opting to register for clinical trials. In a previous pilot study, we found that 45% of minority patients in the community adopted recommendations for medical treatments after exposure to tailored health messages, which compares to 25% who did without such exposure. Assuming a 20% increase in the likelihood of adopting health messages and a sample size of 100, the proposed study will have adequate power for a preliminary test of the hypothesis that exposure to health messages will foster greater uptake of tailored health messages and improvement in clinical trial health literacy level. Achieving the goal of a 20% increase would have an important public health impact regarding adoption of messages about clinical trials. A two-tailed test, with 80% power and $\alpha = 0.05$ comparing 25% to 45% requires 50 participants per arm. The study is powered to assess differences in participation rates between the two arms as well as the mediating effect of individual and contextual factors between tailored clinical trial messages and participation rates, considering a 23% attrition rate.

VI. DATA HANDLING

Confidentiality

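### Fifty per arm gives about 56% power for 25% versus 45%, not the stated 80%, and that calculation leaves no allowance for the stated 23% attrition

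*Combined protocol and SAP*

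**What the plan says.** Section V (Statistical Plan, Power Calculations) makes two power statements.

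- **Effect-size statement.** It takes an effect size of 0.32, labelled d and called medium, with Fisher's exact test and a critical chi-squared of 6.58: "and a sample size of 100, the study will be adequately powered (> 80%) to detect significant differences". The groups are participants likely and not likely to improve in health literacy. It is then extended to registration: "This will also permit detection of a significant increase in the number of participants in the intervention arm opting to register for clinical trials".
- **Two-proportion statement.** A previous pilot found that "45% of minority patients in the community adopted recommendations for medical treatments after exposure to tailored health messages", against 25% without exposure. For a two-tailed test at alpha 0.05 with 80% power, "comparing 25% to 45% requires 50 participants per arm".

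The section closes by saying the study is powered for the difference in participation rates between arms and for mediating effects "between tailored clinical trial messages and participation rates, considering a 23% attrition rate".

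Planned enrolment equals the stated requirement. Under Study Design, Objective 1, "The intervention group (n=50) will have access to culturally tailored website", and the control arm is the same size. Section II.3 "expects to recruit a total of 100 participants from all recruitment strategies over a period of 9 months". The Hypothesis 1 analysis in Section IV uses logistic regression for "registering to participate in clinical trials, contrasting individuals in the two study arms". Registration with ResearchMatch is asked about at 1 month (Section III, data acquisition for objective 1). The last visit is at 3 months.

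**The concern.** A 20-point difference starting from 25% normally needs well over 50 per arm for 80% power, so the printed number looked too small. The enrolment target is also the same as the stated requirement, although the paragraph claims to have considered 23% attrition.

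Section V says a 20-point gain would matter for public health. A reader who accepts 80% power will believe there is a 20% chance of missing such a gain. If the true chance is more than double that, a null result would be read as stronger evidence against the tailored website than the design can supply.

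**Working it through.** **Inputs, all from Section V unless noted:** p1 = 0.25, p2 = 0.45, two-sided alpha 0.05 (z = 1.960), power 80% (z = 0.842), attrition 23%. Allocation is 50:50 (Study Design, Objective 1).

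**1. Trying to reproduce 50 per arm.** The pooled two-proportion formula is

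n = [1.960·√(2·p̄·(1−p̄)) + 0.842·√(p1(1−p1) + p2(1−p2))]² / (p2−p1)²

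With p̄ = 0.35, the roots are √0.455 = 0.6745 and √0.435 = 0.6595. So

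n = (1.3221 + 0.5551)² / 0.04 = 3.5237 / 0.04 = 88.09, that is **89 per arm**.

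Other methods give 86 (unpooled), 88 (arcsine) and 98 (continuity-corrected). A one-sided 0.05 test needs 70. A value near 50 (51 per arm) appears only at two-sided alpha 0.20, which contradicts the text.

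**2. Power with the planned numbers.** The formula is power = Φ{[0.20·√n − 1.3221] / 0.6595}.

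- n = 50: Φ(0.0921/0.6595) = Φ(0.140) = **55.6%**
- n = 50 × 0.77 = 38.5: Φ(−0.0811/0.6595) = Φ(−0.123) = **45.1%**

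If those lost are instead counted as not registered (an assumption, since the plan is silent), the rates become 0.25 × 0.77 = 19.25% and 0.45 × 0.77 = 34.65% at 50 per arm.

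| Method, 25% vs 45%, two-sided 0.05 | 50 per arm | 77 completers | Lost counted as not registered |
|---|---|---|---|
| Chi-squared, formula | 55.6% | 45.1% | 41.0% |
| Chi-squared, exact enumeration | 55.8% | 46–48% | 41.6% |
| Logistic regression, arm only (Wald / likelihood ratio) | 55.1% / 55.8% | 44–48% | not computed |
| Fisher's exact | 47.7% | about 36–41% | 33.7% |

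The exact figures for 77 completers are for 38/39 splits; the Fisher range also covers 38 and 39 in both arms. A one-sided 0.05 test at 50 per arm gives 67.8%.

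**3. Chance of missing the gain (chi-squared formula).** 100 − 55.6 = 44.4% with no loss, and 100 − 45.1 = 54.9% with 23% excluded.

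**4. Enrolment needed for 80% power.** 89/0.77 = 115.6, so 116 per arm. Even if 50 evaluable had been right, 50/0.77 = 64.9, so 65 per arm would have to be enrolled.

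**5. What can be detected with 80% power.** Solving the same formula for p2 gives 25% versus 51.9% at 50 per arm, and 25% versus 55.9% with 77 completers.

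**6. Does the 0.32 statement support N = 100?** Four readings:

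- As Cohen's w on 1 df at critical value 3.84: N = (1.960 + 0.842)²/0.32² = 7.849/0.1024 = 76.6, so 77, and 77/0.77 = 100. The target of 100 may have come from here.
- As w on 1 df at the printed 6.58 (tail probability 0.0103): N = 114, with power 60% at 77 and 74% at 100. The 1 df is my assumption, as the plan states none.
- As a standardised mean difference, which is what d denotes: Φ(0.32·√25 − 1.960) = Φ(−0.36) = 36% at 50 per arm.
- Against the pilot rates: 25% versus 45% is w = 0.20/(2·√(0.35·0.65)) = 0.21. A w of 0.32 starting from 25% implies about 56%, not 45%.

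**The case against.** The best defence concerns attrition. The 23% is not attached to the 25%/45% sentence; it follows in a sentence about the study as a whole. On the w reading, 77 completers out of 100 give 80.2% power, so attrition may have been built into the first calculation. That is plausible, and it is why the attrition point here is confined to the 25%/45% calculation. It does not make that calculation right: the effect is a different one (0.32 against 0.21), the groups compared are not the arms, and the printed critical value does not match.

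A second defence is that Section 1 calls this a pilot and Section V speaks of a preliminary test. A pilot need not have 80% power, but this plan claims it explicitly.

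A third is that the pilot rates concern adoption of treatment recommendations, not registration, and that the planned logistic model includes baseline factors. Both are true. They make the registration figures conditional and approximate. They do not affect the printed sentence, whose inputs do not give 50 per arm for any binary outcome.

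**Conclusion.** The stated requirement is wrong as printed and nothing elsewhere in the document corrects it. For 25% versus 45% at two-sided 0.05, 80% power needs 89 evaluable per arm. The planned 50 per arm gives about 56%, or about 45% if 23% are lost and excluded, and no reasonable test or formula at the stated alpha brings 50 per arm near 80%.

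Applying these figures to the trial assumes that the pilot rates transfer to a binary outcome such as registration, and that an unadjusted chi-squared test approximates the planned logistic regression. The effect of attrition also depends on the visit to which the 23% applies, which the plan does not state. The figures do not describe power for the 1-to-5 willingness item. The sentence must be corrected because it is the explicit justification for the sample size.

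**What to change.** Keep N = 100 and restate Section V.

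1. Replace the 80% sentence with: *50 per arm gives about 56% power for 25% versus 45% on a binary outcome (two-sided 5% chi-squared test, an unadjusted approximation to the planned logistic regression), or about 45% if 23% are lost and excluded.* State the visit to which the 23% refers.
2. Add that, on the same approximation, 80% power exists for about 25% versus 52% at 50 per arm, or about 25% versus 56% with 77 completers.
3. Clarify or replace the sentence with d = 0.32 and critical value 6.58 by one calculation that names the effect measure, test, critical value and groups. Do not extend it to registration by arm unless it applies there.
4. State that the figures assume the pilot's 25% and 45% transfer to registration, and that they do not cover the willingness item.

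Optionally, give the expected 95% confidence interval half-width for the difference between arms: 1.96·√(0.435/50) = 18 points, or 21 points with 77 completers. The claim of power for mediation could also be supported or dropped.

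The cost is protocol wording and a less favourable stated power. Sample size, conduct and planned analysis are unchanged. If the sponsor wants 80% power for this difference after 23% loss, enrolment would have to be 116 per arm; that is a separate design decision.

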Data acquisition for objective 1: We will use a randomized group design, assessing patient-centered outcomes (health literacy, willingness to participate in a clinical trial, willingness to refer others), contrasting participants who were exposed to health messages via NYU's standard clinical trial website (<http://www.med.nyu.edu/oct/home>) [control arm] and those exposed to the newly created culturally and linguistically tailored website [intervention arm]. They will all complete measures at baseline assessing demographics, general health status (Medical Outcomes Study Short Form), baseline health literacy measures (National Assessment of Adult Literacy), and willingness to participate in a clinical trial ("On a scale from 1 to 5, with 1 being 'not at all willing' and 5 being 'very willing', how willing would you be to participate in a clinical trial in the future?" Response anchors will be; not at all willing, somewhat unwilling, neutral, somewhat willing, and very willing).

At the 1-month debriefing, we will reassess participants' willingness to participate in a clinical trial, and ask whether or not they opted to register with ResearchMatch; an online volunteer clinical research registry. These data will help establish a model for future translational and dissemination research. At the end of the 2-year project, we expect to have developed a culturally-tailored clinical trial literacy website that could be widely accessed. There are over 31,000 racial/ethnic minority barbershops, beauty salons, and faith-based organizations across the United States that could use this non-traditional model promoting participation in clinical trials. The long-term goal is to use this infrastructure for dissemination of evidence-based clinical trial health literacy and participation at the community level.

Schedule of Events

The primary aim of this study is to compare the tailored materials to control information only materials that are not tailored to the population being studied. However, before the Intervention/Control study, all messages and online resources will be assessed using cognitive heuristic testing to ensure the website is user friendly and culturally and linguistically tailored to the population. Heuristic testing to ensure cultural and linguistic appropriateness of the resource will be conducted, followed by the Intervention/Control study.

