Our collaborator from SUNY Downstate, [name], will conduct heuristic evaluation and cognitive walkthroughs of all web materials, and then perform standard formative usability testing onsite with 10 representative participants to ensure the site is well-suited to the needs of the intended community. These participants will be recruited from the existing pool of participants from previous RCT's mentioned above..

Participants will be contacted, and recruited for this portion of the study via telephone. Participants will be scheduled into time slots of approximately 40 minutes in duration. Participants will come to CHBC at their assigned timeslot, read and sign the consent form, and then begin the heuristic testing. She will ascertain whether health materials are acceptable and whether they capture daily experiences of potential patients whose lives vignettes intend to portray. She will recommend necessary changes based on log-file analysis that captures computer activity while the participant uses the website. In addition, [name] will ask participants several debriefing questions, such as their experience with the Internet, their willingness to use the resource in the future, and their overall user experience. This will ensure that messages are credible and understandable to the partner community.

Materials will also be presented to stakeholders in our Community Advisory Board for final approval. Once approved, materials will be available for use in the Intervention/Control Study.

Intervention/Control Study

Participants in the Intervention/Control study will be asked to come to the Center for Healthful Behavior Change for three discrete visits, including baseline, 1-month follow up, and 3-month follow up.

Baseline:

- I. Participants will be contacted from our prior IRB approved studies. Potential participants recruited through community locations and events like health fairs will also be contacted. All potential participants will be scheduled into an enrollment slot at which time they arrive at the CHBC ([name]) to fill out baseline surveys and receive study instructions.
- II. When participants arrive, they will be invited to go to either the intervention or control enrolment sessions. These groups will remain separate so as not to cross-contaminate instructions or materials.

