- III. Participants will receive the consent forms, and will be asked to read the documents carefully. Participants will be provided time to call any family or friends, and given the time they need to make an informed decision about participation. The consent forms will be approved by the IRB, and include a request for participant cell phone number and email address. Cell phone is collected so that participants may be sent study reminders, and email is

requested so that the study personnel might share the intervention resource with participants in the control condition at the end of the study. Participants will also be asked if the study team can record the debriefing session. If so, consent will be obtained.

- IV. Participants will take baseline surveys; this will take approximately 25 minute. Next, participants will receive their experimental materials, which include a Wi-Fi enabled tablet that has been pre-loaded with either intervention or control materials on the browser. Participants will receive verbal and paper-based instructions from the research assistant on how to log into the online, tailored website (intervention condition) or how to access the generic informational website (control condition). Participants will be debriefed, thanked for their time, and scheduled for a slot for their 1-month follow up visit. Participants will receive \$25 for their participation.

One-month follow up:

- Participants will return to the Center for healthful Behavior Change at their 1-month follow up appointment. At this time, participants will be instructed to bring their tablets with them to return the device, and take a follow up survey. The survey will take approximately 25 minutes.
- Participants will be thanked for their time, and scheduled for a slot for their for their 3-month follow up visit. Participants will receive \$50 for their participation.

Three-month follow up:

- Participants will arrive at the CHBC for their 3-month follow up to simply take on last, follow up survey. Participants in the intervention condition will receive \$25 for their participation, debriefed, and released from the study.
- Participants in the control condition will also receive \$25 for their participation, debriefed, and instructed that they will receive access to the intervention resources via email after no later than 3 months.

All outcome measures are located in Table 1.

Table 1 Outcome Measures	Baseline	1 months	3 months
Demographic and Clinical Variables	X		

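### Sections IV and V promise a comparison of trial participation rates, but no described outcome records being screened for or joining a trial

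*Combined protocol and SAP*

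**What the plan says.** Two parts of the protocol name participation as the outcome. Section V (Statistical Plan, Power Calculations) closes with: "The study is powered to assess differences in participation rates between the two arms", and extends the claim to mediation of those rates. In Section IV, the analysis for Hypothesis 2 says that structural equation modeling (SEM) will address "the role of tailored messages in improving participation rates in existing clinical trials". It ends with a sentence about finding the patient characteristics that go with improved rates of participation.

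The descriptions of what is collected are different:

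- Study Design, Objective 1 (Background and Significance) lists "willingness to enroll in clinical trials and behavioral intent as well as likelihood of referring others to enroll in such trials", and adds that health literacy is measured before and after exposure.
- Section III, data acquisition for Objective 1, gives a 1-to-5 rating, "how willing would you be to participate in a clinical trial in the future", taken at baseline and again at 1 month. At 1 month staff will also "ask whether or not they opted to register with ResearchMatch; an online volunteer clinical research registry".
- The Hypothesis 1 analysis in Section IV fits a logistic regression for "registering to participate in clinical trials, contrasting individuals in the two study arms and (b) referring others to participate as well".
- The Intervention/Control Study has "three discrete visits, including baseline, 1-month follow up, and 3-month follow up", and the protocol states: "All outcome measures are located in Table 1".

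**The concern.** A participation rate in existing trials describes behavior: the proportion of people who entered a trial. Willingness and intent are attitudes, and joining a volunteer registry is a step that may or may not lead to a trial. If the plan is carried out as worded, a difference in attitudes or sign-up could be reported as a difference in participation, and the mediation model would be said to explain participation. Section III looks ahead to dissemination through more than 31,000 community venues, so an overstated result would carry weight beyond this pilot.

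The planning rates do not supply the missing link. The 25% and 45% in Section V come from an earlier pilot on the uptake of medical treatment recommendations, not from trial entry or registry sign-up.

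**Working it through.** **Step 1. Set the claim against the measures.**

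| Place | Outcome described | Records screening for or joining another trial? |
|---|---|---|
| Study Design, Objective 1 | Willingness, behavioral intent, likelihood of referral, health literacy | No |
| Section III | Health literacy, willingness rating (baseline, 1 month), willingness to refer, ResearchMatch registration (1 month) | No |
| Section IV, Hypothesis 1 | Registering, referring others, health literacy scores | No |
| Table 1 | Demographic and clinical variables, SF-36, Internet self-efficacy, clinical trials literacy, message effectiveness, Clinical Vignette (3 months) | No such row; the vignette is not described |

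Table 1 also has no row for willingness, registration or referral, although the text says that they are assessed.

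**Step 2. Ask whether registration could stand in for participation.** The plan nowhere defines participation as registration. Section II (Recruitment) draws some participants from ResearchMatch itself. Those people may already be registered at entry, yet registration is mentioned only at 1 month and no baseline status is described. A yes at 1 month would therefore mix old and new registrations.

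**Step 3. Check whether the power claim could move to the measured outcomes.** Inputs from Section V: rates 0.25 and 0.45, two-sided α = 0.05, power 80%, 50 per arm, attrition 23%.

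The plan's figure first. With pooled variance under the null:

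n per arm = [1.96·√(2·p̄·(1−p̄)) + 0.842·√(p₁(1−p₁) + p₂(1−p₂))]² / (p₂−p₁)²

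- p̄ = 0.35, so √(2·0.35·0.65) = √0.455 = 0.6745.
- √(0.1875 + 0.2475) = √0.435 = 0.6595.
- n = (1.3221 + 0.5551)² / 0.04 = 3.524 / 0.04 = 88.1, so 89 per arm.

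The stated 50 per arm is not reproduced. A continuity correction gives 98, unpooled variance 86 and the arcsine method 88. A one-sided test still needs 70.

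Power at a given n is Φ[(0.20·√n − 1.3221) / 0.6595]:

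- n = 50: (1.4142 − 1.3221) / 0.6595 = 0.140, so 55.6%.
- After attrition, 50 × 0.77 = 38.5. With 38: (1.2329 − 1.3221) / 0.6595 = −0.135, so 44.6%.

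With Fisher's exact test the figures are 47.7% and 36.4%.

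**Step 4. Could actual enrollment be tested instead?** The documents give no enrollment rate. As assumptions only, 5% versus 10%, 5% versus 15% and 10% versus 20% would give about 15%, 38% and 29% power with 50 per arm. Over that range, an added enrollment item could be descriptive only.

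**The case against.** The best defense is that *participation rates* is loose shorthand. The objectives and hypotheses are worded as likelihood of participating, which the described outcomes can address. The Hypothesis 1 regression contrasts the arms on registering. Earlier in the power paragraph, the plan speaks of intervention-arm participants opting to register. Proximal outcomes are also a legitimate choice for a pilot that offers a preliminary test.

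Much of this stands, and it limits the point. A reader might infer that the trial cannot test its hypotheses. The documents do not support that; only the conclusion about actual participation is out of reach. A reader might also infer that nothing beyond willingness and sign-up is collected. Intent, referral and health literacy are named too, and a Clinical Vignette and a recorded 3-month feedback session are planned, though none is shown to capture trial entry.

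Nor is it proved that no form asks about enrollment. The surveys are not reproduced, the flowchart is not shown, and Table 1 is visibly incomplete despite the statement that it holds all outcome measures. The supportable statement is that no such measure is described.

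The documents also give no basis for saying how many people could join a trial within 1 month, or how often registration leads to enrollment. No participation effect can therefore be derived from a sign-up effect.

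The shorthand reading does not remove the problem. The plan never defines the term, and the SEM sentence refers to existing trials, which registry sign-up does not measure.

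**Conclusion.** The point holds as a mismatch between three sentences (power, SEM, patient characteristics) and the outcomes described. Conclusions about willingness, intent, referral, literacy and registration remain open; a conclusion about actual participation rates does not. This rests on reading the outcome descriptions as complete for trial entry, which the unseen survey forms could change.

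The mismatch has no numerical size of its own, because no participation data are described. The figures in Step 3 bear on the repair: at the plan's own rates, power is about 56% at 50 per arm and about 45% at 38, so renaming the outcome does not carry the 80% with it. That those rates apply to registration or referral is itself an assumption. It should be corrected before analysis, but it does not undermine the trial's usefulness as a pilot.

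**What to change.** 1. In the SEM and patient-characteristics sentences of Section IV and the power sentence of Section V, replace participation rates with the outcomes measured: willingness score, new self-reported ResearchMatch registration, and referral. Limit conclusions to these. Do not attach the 80% power claim to them.
2. Ask ResearchMatch registration status in the baseline survey, before the tablet is handed out, and count only new registrations. People already registered cannot contribute a new one, so the informative number may fall below 50 per arm by an amount the documents do not give.
3. Add one item to the existing 3-month survey: since enrollment, has the participant contacted, been screened for or joined any other clinical trial? Report it descriptively by arm.
4. Add willingness, registration, referral and the new item to Table 1 with their visits.

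The cost is protocol wording and two survey questions, with no extra visit or participant. The headline claim becomes more modest, and 3 months may be short for actual enrollment.
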